2.2.2 Randomization

Eligible subjects will be randomized to one of two treatment groups in a 1:1 ratio:

- SL BUP/NAL SOC background therapy
- SL BUP/NAL + OXD01 digital therapy

Eligible subjects will be randomized on Day 1 through an IRT system.

Each subject will be identified by a unique randomization number assigned by the IRS system on Day 1. Prior to randomization, subjects will be identified by a screening number, assigned when the subject signs the ICF.

2.2.3 Study Treatment and device

- SL BUP/NAL SOC background therapy
- SL BUP/NAL + OXD01 digital therapy for 15-30 minutes, 1-2 times per week

Subjects in both groups will receive the assigned treatment for 24 weeks. Note: No investigational product will be administered as part of this study. Subjects in both groups may also be encouraged to participate in behavioral health therapies in accordance with the Investigator's standard of practice.

2.2.4 Sample Size Determination

Treatment success is defined as the subject having $\geq 80\%$ of urine drug tests negative for opioids plus $\geq 80\%$ of self-reports negative for illicit opioid use (from the TLFB interview at the same visit) from Week 6 to Week 25 of the study. Current literature suggests that the proportion of subjects likely to be successful by this measure while under treatment with the control agent may be approximately 12%. [1] If OXD01 is effective in improving this percentage to 25%, approximately 200 subjects will be required to receive each treatment to provide 90% power to

detect such a difference at an $\alpha = 0.05$ level (Fisher's Exact Test). Approximately 510 opioid dependent males and females will be screened to randomize approximately 400 subjects.

3 STATISTICAL METHODOLOGY

3.1 General Considerations

3.1.1 Analysis Day

Analysis day will be calculated from the date of first use of study device. The day of the first use of study device will be Day 1, and the day immediately before Day 1 will be Day -1. There will be no Day 0.

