#### ***3.1.2 Study Treatments***

On study Day 1, subjects stabilized on SL BUP/NAL SOC background therapy will be randomized to SL BUP/NAL alone, or to SL BUP/NAL plus the OXD01 digital therapeutic. A stabilized subject will have completed SL BUP/NAL induction, with physical withdrawal symptoms reduced so the subject is able to fully participate in OXD01 training, if randomized to that treatment group. Induction with SL BUP/NAL and titration to a maintenance dose that suppresses withdrawal signs and symptoms is described in the product information under Dosage and Administration and can be implemented in accordance with the Investigator's standard of practice. Note: No investigational product will be administered as part of this study.

Subjects randomized to SL BUP/NAL plus OXD01 will be trained to use OXD01 on Day 1 as directed in the OXD01 Clinician User Guide and will begin to access the therapeutic counseling modules for 15-30 minutes, 1-2 times per week as instructed. Randomization and OXD01 training should be conducted as soon as the subject is clinically stable, with physical withdrawal symptoms managed and the subject able to fully participate in the process, but no greater than 14 days from the first dose of SL BUP/NAL induction.

Subjects in both groups will use the assigned treatment for 24 weeks.

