#### 6.13 Randomization and Allocation to Treatment, Subject Identification Number

Eligible subjects will be randomized on Day 1 through an IRT system (separate instructions will be provided).

Each subject will be identified by a unique randomization number assigned by the IRS system on Day 1. Prior to randomization, subjects will be identified by a screening number, assigned when the subject signs the ICF.

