3.1.2 Analysis Visits

Scheduled visits will be assigned to analysis visits as recorded on the electronic case report form (eCRF). Unscheduled visits recorded on the eCRF will not be re-assigned and will remain labeled as unscheduled.

Early termination (ET) visits will be assigned to analysis visits according to the following visit windows:

| Analysis Visit | Target Analysis Day | Low Analysis Day | High Analysis Day |
|----------------|---------------------|------------------|-------------------|
| Week 2 | 8 | 2 | 11 |
| Week 3 | 15 | 12 | 18 |
| Week 4 | 22 | 19 | 25 |
| Week 5 | 29 | 26 | 32 |
| Week 6 | 36 | 33 | 39 |
| Week 7 | 43 | 40 | 46 |
| Week 8 | 50 | 47 | 53 |
| Week 9 | 57 | 54 | 60 |
| Week 10 | 64 | 61 | 67 |
| Week 11 | 71 | 68 | 74 |
| Week 12 | 78 | 75 | 81 |
| Week 13 | 85 | 82 | 88 |
| Week 14 | 92 | 89 | 95 |
| Week 15 | 99 | 96 | 102 |
| Week 16 | 106 | 103 | 109 |
| Week 17 | 113 | 110 | 116 |
| Week 18 | 120 | 117 | 123 |
| Week 19 | 127 | 124 | 130 |
| Week 20 | 134 | 131 | 137 |
| Week 21 | 141 | 138 | 144 |
| Week 22 | 148 | 145 | 151 |
| Week 23 | 155 | 152 | 158 |
| Week 24 | 162 | 159 | 165 |
| Week 25 | 169 | 166 | |

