Concomitant medications will be coded to anatomical therapeutic chemical (ATC) class and preferred term using the WHO Drug Dictionary version March 2021G B3. For summary purposes, medications will be considered prior medications if they stopped prior to the first use of study device (Day 1) and concomitant medications if they were taken at any time after the first use of study device (i.e. started prior to Day 1 and were ongoing or started after Day 1).

If a medication has incomplete start or stop dates, dates will be imputed to determine whether a medication should be considered prior or concomitant. If a medication start date is incomplete, the first day of the month will be imputed for missing day and January will be imputed for

missing month. If a medication stop date is incomplete, the last day of the month will be imputed for missing day and December will be imputed for missing month. Incomplete start and stop dates will be listed as collected without imputation.

Counts and percentages of subjects taking concomitant medications by ATC class and a preferred term will be summarized by treatment based on the Safety Population.

3.3.8 *Study Device Compliance*

Dosing instructions will be reviewed and subjects will be interviewed to assess treatment compliance at the following Visits: Weeks 2-5, 7, 9, 11, 13, 17, 21, and 25.

Percent compliance of study device OXD01 will be calculated as the number of OXD01 sessions taken / the number of expected OXD01 sessions taken. Percent compliance to the study device regimen will be summarized based on the Safety Population with descriptive statistics and with counts and percentages of subjects with compliance in the following categories:

- <50%
- 50-80%
- 80-100%
- >100%

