2. Concomitant medications ongoing on Day 1 will be recorded.
3. As soon as the subject is clinically stable on SL BUP/NAL with physical withdrawal symptoms managed, and the subject able to fully participate in OXD01 training, but no greater than 14 days from the first dose of SL BUP/NAL induction.

Schedule of Events (Continuous): Weeks 13-25, Early Termination

| Evaluation | Treatment | | | | | | | Early Termination |
|--|-------------------|--------------------------------|--------------------|-----------------------------------|--------------------|----------------------------------|--------------------|-------------------|
| | Week 13 Day 85 | Week 14/15/16 Day 92/99/106 | Week 17 Day 113 | Week 18/19/20 Day 120/127/ 134 | Week 21 Day 141 | Week 22/23/24 Day 148/155/162 | Week 25 Day 169 | |
| Window | ± 1 Day | ± 1 Day | ± 1 Day | ± 1 Day | ± 1 Day | ± 1 Days | ± 1 Day | |
| Informed consent | | | | | | | | |
| Demographics | | | | | | | | |
| Inclusion/exclusion criteria review | | | | | | | | |
| Medical history | | | | | | | | |
| Opioid use history | | | | | | | | |
| Confirm diagnosis - OUD ¹ | | | | | | | | |
| Previous treatments for OUD | | | | | | | | |
| Concomitant medications ² | | | | | | | | |
| Physical examination | | | | | | | | |
| Vital signs | | | | | | | | |
| Urine drug screen | X | X | X | X | X | X | X | |
| QFI | | | | | | | X | X |
| TLFB interview – drugs and alcohol | | | | | | | X | X |
| TLFB interview – drugs | X | X | X | X | X | X | | |
| Review study restrictions with subject | X | | X | | X | | | |
| Randomization – IRS ³ | | | | | | | | |
| OXD01 – subject training ³ | | | | | | | | |
| Opioid craving VAS | X | | X | | X | | X | X |
| QIDS-SR | | | | | | | X | X |
| CGI-S | X | | | | | | X | X |
| CGI-I | X | | | | | | X | X |
| Review behavioral health therapies | X | | X | | X | | X | X |
| MAT compliance assessment/counseling | X | | X | | X | | X | X |
| OXD01 compliance assessment/counseling | X | | X | | X | | X | X |
| End of study interview | | | | | | | X | X |
| Adverse Events | X | X | X | X | X | X | X | X |

OUD – opioid use disorder; QFI – Quantity-Frequency Index; TLFB – timeline followback method; IRS – interactive response system; MAT – medication-assisted treatment; VAS – visual analog scale; QIDS-SR – Quick Inventory of Depression Symptoms, Self-Report; CGI-S/I – clinical global impression severity/improvement

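### The SAP starts the analysis clock at first device use, so it has no rule for placing control early-termination visits; separately, it treats AEs with missing start dates as device related unless a partial date rules that out

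*SAP*

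**What the plan says.** **Analysis day.** SAP 3.1.1: "Analysis day will be calculated from the date of first use of study device". It calls that day Day 1 and gives no alternative for a subject without a device. The clock drives SAP 3.1.2, where "Early termination (ET) visits will be assigned to analysis visits according to the following visit windows"; the table runs from Week 2 (days 2 to 11) to Week 25 (day 166 onward). Other visits do not use the clock: "Scheduled visits will be assigned to analysis visits as recorded on the electronic case report form (eCRF"). SAP 3.3.7 repeats the device anchor: "medications will be considered prior medications if they stopped prior to the first use of study device (Day 1").

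Only the OXD01 arm uses the application (SAP 2.2.1 and 2.2.3). Elsewhere Day 1 means something else. Protocol 3.1.2 has "On study Day 1, subjects stabilized on SL BUP/NAL SOC background therapy will be randomized to SL BUP/NAL alone" or to the combination, and SAP 2.2.2 has "Eligible subjects will be randomized on Day 1 through an IRT system", as does Protocol 6.13. SAP 3.1.3 sets baseline at Study Day 1.

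**Adverse events.** SAP 3.5.1 treats an AE with a missing start date as device related, unless a partial date rules that out. A further sentence takes an AE with missing causality as related. Neither rule is limited to one arm. In Protocol 7.4 the investigator rates relatedness to the device, and a start date is recorded for every AE. The overview list in SAP 3.5.1 counts TEAEs in two rows, but the SAP text neither defines the term nor lists the abbreviation.

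**The concern.** (a) A literal reading gives controls no analysis day, so none of the 24 windows can be applied to their ET visits, while ET visits of OXD01 subjects who used the application can be placed. Under the schedule "Schedule of Events (Continuous): Weeks 13-25, Early Termination" in SAP Appendix A, the ET visit collects the self-report interview, craving VAS, CGI-S and CGI-I. Some of these feed secondary endpoints that SAP 3.4.2 tests in order, with CGI sixth and craving seventh. A data-handling rule that works in one arm only should not stand in an open-label comparison, even where few values are involved.

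(b) A start date bears on timing, not on cause. The missing-date rule can put an AE that the investigator rated not related, or an AE in a control subject who has no device, into the device-related rows of the AE tables. AE reporting starts at consent, so an undated event from before randomisation could also land there.

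**Working it through.** The plan gives no estimate of how many ET visits are exposed. Its only figures here are the window limits, so those are checked first.

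**1. Which Day 1 the windows fit.** The target for Week k is 7 × (k − 1) + 1: Week 6 gives 36 and Week 25 gives 169. These match the table and the visit days in Protocol Tables 1 and 2, which run from randomisation. Counted from randomisation, every ET day from day 2 falls in exactly one window: Week 2 has 10 days, Weeks 3 to 24 have 22 × 7 = 154, and Week 25 starts at day 166.

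**2. Possible ET days.** Days 2 to 168 give 10 + 154 + 3 = 167. (The Week 25 window has no upper limit; the count stops the day before the Day 169 target.)

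**3. Days on which an ET value falls in a window used for an endpoint.** The upper bound counts the whole window. The narrower count assumes the scheduled visit was attended on its target day, so only ET days up to the target matter.

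| Endpoint | Windows | Upper bound | Narrower count |
|---|---|---|---|
| CGI | Weeks 13, 25 | 7 + 3 = 10 (6.0%) | 4 + 3 = 7 (4.2%) |
| Craving VAS | Weeks 5, 9, 13, 17, 21, 25 | 35 + 3 = 38 (22.8%) | 20 + 3 = 23 (13.8%) |
| Self-report | Weeks 6–25 | 133 + 3 = 136 (81.4%) | 76 + 3 = 79 (47.3%) |
| Week 25 status | Week 25 | 3 (1.8%) | 3 (1.8%) |

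**4. Control values at risk.** The documents give no ET rate. Assume 20%, 40% or 60% of 200 controls have an ET visit (40, 80 or 120), spread evenly over the 167 days. Values at risk = number with ET × days ÷ 167.

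- CGI: 1.7, 3.4 or 5.0; upper bound 2.4, 4.8 or 7.2.
- Craving VAS: 5.5, 11.0 or 16.5; upper bound 9.1, 18.2 or 27.3.
- Self-report: from 40 × 79 ÷ 167 = 18.9 to 120 × 136 ÷ 167 = 97.7. Against 200 × 20 = 4,000 scheduled control reports in Weeks 6 to 25, that is 0.5% to 2.4%. Each is one of a subject's 20 reports, so it moves that subject's percentage by at most 5 points.
- Week 25 completer status: at most 120 × 3 ÷ 167 = 2.2 controls. Day 168 also lies inside the scheduled Week 25 visit window (169 ± 1); without it the figure is 120 × 2 ÷ 167 = 1.4.

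**5. Conditions on the last two lines.** The self-report figure applies only if an ET report is not treated as falling after withdrawal. SAP 3.4.1 imputes reports after withdrawal as positive for the primary endpoint; if that extends to this endpoint and covers ET reports, they are positive in both arms and no asymmetry remains. The completer figure applies only if an ET visit windowed to Week 25 counts as the Week 25 visit. The SAP states neither.

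**6. What the anchor does not reach.** Scheduled visits keep their eCRF label. Baseline is Study Day 1. No urine drug screen is marked at ET (SAP Appendix A), and SAP 3.4.1 imputes results after withdrawal as positive, so the primary endpoint is essentially unaffected. The medication split hardly matters, because only medications ongoing on Day 1 are recorded (SAP 3.3.7).

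**7. Adverse events.** No count is possible from the documents. Since Protocol 7.4 calls for a start date on every AE, cases should be few.

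**The case against.** The strongest reply is that the intent is plain. The window targets follow the randomisation schedule, Day 1 is randomisation in several places, and SAP Section 7 promises separate programming specifications. The likely outcome is that a programmer uses the randomisation date and no control value is lost. That stands as a limit on the practical risk. It does not make the text correct: SAP 3.1.1 states a different rule, and a programming document should implement the SAP rather than override it.

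On AEs, the reply is that the missing-date rule has an exception for partial dates, errs towards reporting more device-related events, and will rarely be used. All of that is fair. The exception cannot help when the date is wholly missing, and the rule still applies to subjects who have no device.

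A reader might infer more than the documents support:

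- *That the asymmetry favours OXD01 through completers and self-reports.* This needs both unstated readings in step 5.
- *That the primary comparison or baseline is compromised.* Step 6 shows otherwise.
- *That ET visits in the OXD01 arm are placed in the wrong week because first use lags randomisation.* Training is planned for Day 1, with access to the modules beginning then, and the documents give no lag.

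**Conclusion.** Both parts hold on the text, and both are minor SAP corrections. (a) The stated anchor cannot be applied to controls, or to an OXD01 subject who never opens the application, and it conflicts with Day 1 as used elsewhere. The clear exposure is CGI and craving VAS values from ET visits, with unknown direction: at most about 2 to 7 and 9 to 27 control values respectively. Those counts rest on the assumed 20% to 60% ET rate, an even spread of ET days and a literal reading of SAP 3.1.1. Effects on self-reports and completer status are conditional as well as small, and no directional claim is made for any endpoint. (b) The missing-date rule wrongly turns a question of timing into one of causality, but only descriptive AE tables are affected.

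**What to change.** **(a)** Replace the anchor in SAP 3.1.1 with: *Analysis Day 1 is the date of randomisation (Study Day 1) for both arms.* Apply it in 3.1.2 and 3.3.7.

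**(b)** In SAP 3.5.1, replace the missing-date sentence with: *AEs with missing start dates are treated as starting on or after Day 1 (treatment-emergent) unless the partial date excludes it; device relatedness is as assessed by the investigator.* Define a TEAE as an AE that starts or worsens on or after Day 1. For missing causality, assume relatedness to the device in the OXD01 arm only, count control-arm AEs as not device related, and keep the assumed-related rule for BUP/NAL in both arms.

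The cost is a few sentences, with no new data and no change to the primary analysis. One limit: Protocol 7.4 records a single maximum intensity per event, so worsening of an AE that began before Day 1 can be identified only where the record shows it. SAP Section 1 provides for finalisation before database lock; a change made after lock would have to be documented in the clinical study report.

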3.1.2 Analysis Visits

Scheduled visits will be assigned to analysis visits as recorded on the electronic case report form (eCRF). Unscheduled visits recorded on the eCRF will not be re-assigned and will remain labeled as unscheduled.

Early termination (ET) visits will be assigned to analysis visits according to the following visit windows:

| Analysis Visit | Target Analysis Day | Low Analysis Day | High Analysis Day |
|----------------|---------------------|------------------|-------------------|
| Week 2 | 8 | 2 | 11 |
| Week 3 | 15 | 12 | 18 |
| Week 4 | 22 | 19 | 25 |
| Week 5 | 29 | 26 | 32 |
| Week 6 | 36 | 33 | 39 |
| Week 7 | 43 | 40 | 46 |
| Week 8 | 50 | 47 | 53 |
| Week 9 | 57 | 54 | 60 |
| Week 10 | 64 | 61 | 67 |
| Week 11 | 71 | 68 | 74 |
| Week 12 | 78 | 75 | 81 |
| Week 13 | 85 | 82 | 88 |
| Week 14 | 92 | 89 | 95 |
| Week 15 | 99 | 96 | 102 |
| Week 16 | 106 | 103 | 109 |
| Week 17 | 113 | 110 | 116 |
| Week 18 | 120 | 117 | 123 |
| Week 19 | 127 | 124 | 130 |
| Week 20 | 134 | 131 | 137 |
| Week 21 | 141 | 138 | 144 |
| Week 22 | 148 | 145 | 151 |
| Week 23 | 155 | 152 | 158 |
| Week 24 | 162 | 159 | 165 |
| Week 25 | 169 | 166 | |

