3.4 Efficacy Assessment

Efficacy data will be summarized by randomized treatment based on the FA Population. The primary efficacy endpoint will also be summarized based on the mFA Population.

3.4.1 *Primary Endpoints Analysis*

The primary objective of the study is to determine whether the combination of SL BUP/NAL SOC background therapy and the digital therapeutic OXD01 is superior to SL BUP/NAL alone to reduce opioid use, as measured by the treatment success rate. Treatment success is defined as the subject having $\geq 80\%$ of urine drug tests negative for opioids plus $\geq 80\%$ of self-reports negative for illicit opioid use (from the TLFB interview at the same visit) from Week 6 to Week 25. Each subject will be evaluated as a success or failure for this metric and the proportion of subjects in each group demonstrating $\geq 80\%$ of urine drug tests negative for opioids plus negative self-reports for illicit opioid use (from the TLFB interview) will be tested using chi-squared test. Count and percentage of the subjects with treatment success will be summarized by treatment based on FA Population.

If the subject withdrew the study, then the urine drug tests for opioids and self-reports for illicit opioid use after withdrawal will be imputed as positive. If the subject completed the study with any missing visit, then the urine drug tests for opioids and self-reports for illicit opioid use for the missing visit will be imputed as positive.

Sensitivity analysis 1

As supportive analyses to the primary analysis for the primary endpoint, sub-group analysis using a similar chi-squared test as described above will be repeated for the following factors:

- Percentage of subjects meeting primary endpoint by reported compliance rate or who achieved greater than 80% completion of the visits during Week 6 to Week 25
- Subjects who took the dose of buprenorphine versus retention.
 - Target dose or lower: ≤ 16 mg buprenorphine for Suboxone or equivalent formulation; or ≤ 11.4 mg Zubsolv
 - Higher dose than target dose: > 16 mg buprenorphine for Suboxone or equivalent formulation; or > 11.4 mg Zubsolv
- Subjects who received additional behavioral health services

Sensitivity analysis 2

As supportive analyses, the primary endpoint and key secondary endpoints will be performed using the similar statistical methods based on mFA Population.

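### A negative result at a visit labelled unscheduled cannot fill a missed week, and the missed week is then scored positive in the primary endpoint

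*SAP*

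**What the plan says.** SAP 3.1.2 handles three kinds of visit in three ways.

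- Scheduled visits: "Scheduled visits will be assigned to analysis visits as recorded on the electronic case report form (eCRF". The eCRF label decides the week, and no analysis window is applied.
- Unscheduled visits: "Unscheduled visits recorded on the eCRF will not be re-assigned and will remain labeled as unscheduled".
- Early termination visits: "Early termination (ET) visits will be assigned to analysis visits according to the following visit windows". The table that follows gives each week from Week 6 to Week 24 a contiguous window of its target day plus or minus 3 days. Week 25 starts at Day 166 and has no upper limit.

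SAP 3.4.1 defines success over Week 6 to Week 25 as at least 80% negative urine tests plus at least 80% "of self-reports negative for illicit opioid use (from the TLFB interview at the same visit) from Week 6 to Week 25". It then gives the missing-data rule. "If the subject completed the study with any missing visit", both the urine result and the self-report "for the missing visit will be imputed as positive". For a subject who withdraws, results "after withdrawal will be imputed as positive".

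The SAP does not define a missing visit. It does not say whether an unscheduled result may stand in for a missed week, or whether it enters the percentage as an extra test. Neither sensitivity analysis in SAP 3.4.1 changes the visit rule.

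**The concern.** Scoring a missing visit as positive is a usual convention in opioid-use trials when nothing is known about the week. Here something may be known. If the scheduled visit is absent and the site records a negative urine test and self-report a few days away as unscheduled, the result belongs to no week, and the empty week is scored positive. For any one subject the error runs one way, because an unscheduled positive would be scored positive anyway.

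The situation is foreseeable. The schedules of events allow plus or minus 1 day per weekly visit. Protocol 6.2 expects quarantines, site closures and travel limits, and it excludes urine collection from telemedicine. The SAP itself has a rule for unscheduled visits.

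At stake is whether a clerical label, applied by staff at 30-35 sites, decides success or failure for subjects near the 80% threshold.

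**Working it through.** **Inputs.** Figure 1 lists evaluation visits at Weeks 7, 9, 11, 13, 17, 21 and 25 within the endpoint period (7 visits), and UDS/interview-only visits at Weeks 6, 8, 10, 12, 14-16, 18-20 and 22-24 (13 visits). SAP 2.2.4 gives 12% against 25% success, about 200 per arm, α = 0.05 and 90% power by Fisher's exact test. SAP 3.1.5 makes the test two-sided. SAP 3.4.1 names the chi-squared test.

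**The plan's own figure.** Exact enumeration of Fisher's test at 200 per arm gives 90.4% power, so the stated figure reproduces. For the chi-squared test, the normal approximation is Φ{[0.13√200 − 1.96√(2 × 0.185 × 0.815)] / √(0.12 × 0.88 + 0.25 × 0.75)} = Φ(1.408) = 92.0%. That is the baseline below. The sample size does not depend on the visit rule.

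**Threshold.** 7 + 13 = 20 visits, and 0.80 × 20 = 16 negatives needed, so 4 positives are tolerated.

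**Individual subjects.** An affected week is one where the scheduled visit is missed and both negatives were recorded at an unscheduled visit.

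- 20 observed negatives with 5 affected weeks: 15/20 = 75%, failure. If those results filled their weeks: 20/20, success.
- The same subject with 4 affected weeks: 16/20 = 80%, still a success.
- 3 true positives with 2 affected weeks: (20 − 3 − 2)/20 = 75%, failure. If filled: 17/20 = 85%, success.

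**Chance of success with m weeks lost to the label.** Assume independent visits with per-visit negative probability p. As written, the chance is P(X ≥ 16) with X ~ Bin(20 − m, p). The m = 0 column is also the value after the repair.

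| p | m=0 | m=1 | m=2 | m=3 | m=4 | m=5 |
|---|---|---|---|---|---|---|
| 0.80 | 0.630 | 0.455 | 0.271 | 0.118 | 0.028 | 0 |
| 0.90 | 0.957 | 0.885 | 0.734 | 0.482 | 0.185 | 0 |
| 0.95 | 0.997 | 0.987 | 0.942 | 0.792 | 0.440 | 0 |

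**Trial level, hypothetical.** The documents give no share of affected weeks, so a share u, equal in both arms, is assumed. Further assumptions: 20-40% of subjects drop out and count as failures; among the rest, the per-visit negative probability follows a beta distribution with precision between 0.3 and 5; and each arm's mean is set so that success is 12% or 25% at u = 0. Each visit then counts as negative with probability p(1 − u), and power is recomputed with the formula above.

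| u | Power at 200 per arm |
|---|---|
| 0 | 92.0% |
| 2% | 90.5-91.9% |
| 5% | 87-92% |
| 10% | 78-90% |

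The width of each range comes from the assumed dropout and precision, which the documents do not fix.

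**The case against.** The strongest reply is that an ordinary late visit is not harmed. Scheduled visits follow their eCRF label without a window, so a Week 10 visit held several days late but entered as Week 10 keeps its result. The plus or minus 1 day is a conduct tolerance, and nothing in the documents turns a visit outside it into an unscheduled one. The protocol describes no unscheduled visit or unscheduled UDS. This stands, and it narrows the point to weeks where the scheduled visit is absent and the result carries the unscheduled label. An unscheduled visit made in addition to the scheduled one overwrites nothing.

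A second reply is that failing an unattended scheduled test is conservative, treats both arms alike, and stops subjects choosing their own test day. That is a fair reason to keep the strict rule as a sensitivity analysis. It does not explain why the same section gives early termination visits a window.

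A third is that the existing windows cannot simply be reused. SAP 3.1.1 counts analysis day from first device use, which control subjects do not have, and Week 25 is open-ended. Both stand and are built into the fix.

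A reader might also infer that, because the trial is open-label, the rule biases the comparison or inflates type I error. The documents do not support that. Nothing in them suggests that labelling differs by arm, reversing an assumed split reverses the bias, and any figure would depend on assumed heterogeneity.

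**Conclusion.** The point holds in a conditional form. Read literally, the two rules can turn an observed negative into a positive, and no other provision prevents it. The threshold results (failure at 5 affected weeks for a fully negative subject, at 2 for one with 3 true positives) follow from the visit schedule. They rest on reading a week with no scheduled visit as missing. If unscheduled tests were instead counted as extra tests, the negative would be diluted rather than replaced; the SAP should say which applies.

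The effect on the trial is unknown, because the frequency of such weeks is not given. Under the assumptions shown, equal loss of 5% of weeks leaves power near the planned 90%, and 10% lowers it to roughly 78-90%. These are scenarios. No change to the sample size is needed. The reason to act is that the plan leaves a primary outcome to a site's label, and the correction is cheap before lock.

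**What to change.** Before database lock, amend SAP 3.1.2 and 3.4.1 as follows.

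1. When the scheduled visit for a week is missing, the unscheduled UDS plus self-report closest to the target day within that week's existing window fills the week.
2. An existing scheduled result is never replaced, so a retest cannot overturn a positive.
3. Positive is imputed only if no result falls in the window.
4. Count analysis day from randomization (Study Day 1) instead of first device use, so that the windows mean the same in both arms.
5. Give the Week 25 window an upper limit, for example Day 172 (169 + 3, matching the other weeks).
6. Report the current rule, with unscheduled results ignored, as a sensitivity analysis of the primary endpoint.

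The cost is a few SAP sentences and some extra programming, with no new data. The downside is that some results will come from off-schedule days; the sensitivity analysis shows whether that matters.
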